7.0 Drug information

7.1 Description

The drug product, APN401, is a suspension of viable PBMCs transfected with siRNA in order to reduce Cbl-b protein levels of the respective patient (autologous administration) in saline

7.2 How supplied

Each dose of APN401 contains autologous PBMCs transfected with siRNA in order to reduce Cbl-b protein levels suspended in saline

7.3 Side effects

Infusions of APN401 have been well tolerated. Grade 3 or 4 toxicities attributable to treatment were not observed. Chills are the most common toxicity. These manifested at the completion of the 30 minute infusion and responded to meperidine. Transient lymphopenia, attributed to the leukapheresis, was also observed. Anemia, anorexia, dyspnea, fatigue, fever, hyponatremia, nausea, and myalgia have also been observed.

7.4 Storage and handling

Storage is not recommended. The infusion bag can be maintained at room temperature for up to three hours after release from the laboratory. APN401 should not be infused if maintained more than three hours at room temperature. APN401 is **not** routinely tested for transmissible infectious diseases and may transmit diseases to health care professionals handling the product. Universal precautions should be followed.

7.5 Administration

APN401 is administered at 50×10^6 /kg via intravenous infusion over a period of approximately 30 minutes. **Do not use a cell filter.**

7.6 Cell Processing

Cell processing is performed in the Blood and Bone Marrow Transplant Lab in the North Tower at WFBMC. The BMT lab is not accredited for this purpose and does not have responsibility for the procedures as part of this study within the laboratory. The research team, which includes the PI and an experienced technician, is responsible for the safety, purity and potency of the cellular products under protocol.

8.0 Toxicity Criteria and Adverse Event Reporting

8.1 Adverse event definition

An adverse event is any physical or clinical change or disease experienced by the subject at any time during the course of the study, whether or not considered related to the use of the study drug. This includes the onset of new illness and the exacerbation of pre-existing

Safety and Immunologic Activity of Multiple Infusions of APN401
Wake Forest Baptist Comprehensive Cancer Center
CCCWU 03716

conditions. Disease-related symptoms that do not increase in severity or frequency from baseline are not considered adverse events.

All toxicity should be graded according to the NCI Common Terminology Criteria for Adverse Events (CTCAE) version 4.0. Adverse events will be recorded on an ongoing basis and up to 2 months following the administration of the test drug. All appropriate treatment areas should have access to a copy of the CTCAE version 4.0. A copy of the CTCAE version 4.0 can be downloaded from the CTEP web site (<http://ctep.cancer.gov>).

- **‘Expectedness’:** AEs can be ‘Unexpected’ or ‘Expected’ (see Section 7.3 above) for expedited reporting purposes only.

- **Attribution** of the AE:

Definite – The AE **is clearly related** to the study treatment.

Probable – The AE **is likely related** to the study treatment.

Possible – The AE **may be related** to the study treatment.

Unlikely – The AE **is doubtfully related** to the study treatment.

Unrelated – The AE **is clearly NOT related** to the study treatment.

8.2 Dose limiting toxicity (DLT)

DLT is defined as

- 8.2.1 CTCAE grades 3-5 allergic reactions related to study cell infusion
- 8.2.2 CTCAE grades 3 and greater autoimmune reactions other than that vitiligo
- 8.2.3 CTCAE grades 3 and greater organ toxicity (cardiac, dermatologic, gastrointestinal, hepatic, pulmonary, renal/genitourinary or neurologic) not pre-existing or due to the underlying malignancy and occurring within 30 days of study product infusion
- 8.2.4 Treatment-related death within 8 weeks of the study cell infusion

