research technologist. APN401 is also cultured for microbial growth. The final (14-day incubation) sterility test results are not available at the time of infusion. If the sterility results become positive for microbial contamination after APN401 has been approved for infusion, the treating physician will be informed and testing to identify the microorganism as well antibiotic sensitivity testing on recovered microorganisms will be performed. The clinical investigator should evaluate the subject for any signs of infection that may be attributable to the product sterility failure. Additional information from the physician in order to determine the source of contamination may be necessary. See section 8.5.1 for the reporting requirement for sterility failure.

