8.3 Safety and toxicity reporting requirements

The Safety and Toxicity Reporting Committee (STRC) is responsible for reviewing SAEs for WFBCCC Institutional studies as outlined in Appendix C. STRC currently requires that all unexpected 4 and all grade 5 SAEs on these trials be reported to the STRC for review. Any grade 3 to 5 product infusion reactions must also be reported. All WFBCCC Clinical Research Management (CRM) staff members assisting a Principal Investigator in investigating, documenting and reporting an SAE that qualifies for STRC reporting are responsible for informing a clinical member of the STRC – as well as the entire committee – via the email notification procedure of the occurrence of an SAE.

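### The dose limiting toxicity definition in Section 8.2 is narrower in scope than the grade 3-4 toxicity event to which Section 11 applies the same limits and stopping probabilities, so one set of patients can pass one rule and fail the other

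*Combined protocol and SAP*

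**What the plan says.** Section 8.2 gives four routes to a DLT:

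- Allergy, in item 8.2.1, which names "CTCAE grades 3-5 allergic reactions related to study cell infusion".
- Autoimmunity, in item 8.2.2, from grade 3 upward and with vitiligo excepted.
- Organ damage, in item 8.2.3, which names "CTCAE grades 3 and greater organ toxicity (cardiac, dermatologic, gastrointestinal, hepatic, pulmonary, renal/genitourinary or neurologic". It applies for 30 days after an infusion and leaves out conditions already present and effects of the cancer itself.
- Death, in item 8.2.4, which names "Treatment-related death within 8 weeks of the study cell infusion".

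There is no hematologic, constitutional, metabolic, musculoskeletal, infection or general infusion-reaction item, and no catch-all for other severe related events.

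Other sections describe the product's risks more broadly. Section 7.3 says "Chills are the most common toxicity", mentions transient lymphopenia, and adds: "Anemia, anorexia, dyspnea, fatigue, fever, hyponatremia, nausea, and myalgia have also been observed". Section 8.3 uses a different term from 8.2.1: "Any grade 3 to 5 product infusion reactions must also be reported". Section 5.4.5 accepts that "The final (14-day incubation) sterility test results are not available at the time of infusion".

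The limits are then attached to different events. The synopsis and Section 5.1.3 count DLTs against >1/6 and >3/12. Sections 11.3.2 and 11.4.1 use the same cut-offs for grade 3-4 toxicity, with no restriction by organ or cause. Section 5.1.2 applies >1/6 to toxicity worded as exceeding grade 3 or 4; read literally, that may leave grade 3 out.

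**The concern.** The limit after six patients decides whether the trial expands, and the limit over all patients decides whether APN401 is called tolerable. If the event counted for expansion differs from the event counted for tolerability, the outcome depends on which section the team opens. A patient with a severe infusion reaction that is neither allergic nor accompanied by listed-organ toxicity counts under Section 11 and not under Section 5.1.3.

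The protocol gives reasons to expect such events to be the disputed ones: most of the toxicities it names for this product sit outside the DLT classes, and infusion reactions are singled out for reporting. The stopping probabilities in Section 11 would reassure a reader about a rule they do not describe.

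**Working it through.** **1. Named toxicities set against the DLT classes.** Section 7.3 names ten.

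| Section 7.3 term | Class in 8.2.3 |
|---|---|
| Dyspnea | Pulmonary |
| Nausea | Gastrointestinal |
| Anorexia | Gastrointestinal, arguably |
| Chills, fever, fatigue | None |
| Lymphopenia, anemia | None |
| Hyponatremia | None |
| Myalgia | None |

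Seven of ten match no class, or eight if anorexia is not treated as gastrointestinal. This counts terms. It says nothing about how often severe events of each type occur.

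**2. Section 11 stage 1 figures reproduced.** Stopping requires at least 2 of 6 patients with the event. With per-patient rate p:

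P(stop) = 1 − (1−p)^6 − 6p(1−p)^5

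- p = 0.10: 1 − 0.5314 − 0.3543 = 0.1143. The plan states 11% (11.3.2) and 11.4% (11.4.1).
- p = 0.40: 1 − 0.0467 − 0.1866 = 0.7667. The plan states 76.7%.

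Both figures are right for the event they name, grade 3-4 toxicity.

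**3. Both rules applied to the same patients.** Suppose two of the first six have grade 3 fever and rigors, not allergic or autoimmune, with no grade 3 or greater toxicity in a listed organ.

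- Sections 11.3.2 and 11.4.1: 2/6 exceeds 1/6, so there is no expansion and the product is not tolerable.
- Synopsis and Section 5.1.3: 0/6 DLTs, so expansion proceeds.
- Section 5.1.2: unclear, because of its wording.

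**4. What the DLT rule does to the stopping probability.** Assume a true grade 3-4 rate of 40%, and that a share s of affected patients also meets Section 8.2. The documents do not give s. The DLT rate is 0.40 × s, and the formula in step 2 gives:

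| s | DLT rate | Stage 1 stop probability |
|---|---|---|
| 1 | 0.40 | 76.7% |
| 0.75 | 0.30 | 1 − 0.1176 − 0.3025 = 58.0% |
| 0.50 | 0.20 | 1 − 0.2621 − 0.3932 = 34.5% |
| 0.25 | 0.10 | 1 − 0.5314 − 0.3543 = 11.4% |

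**5. Does the second stage recover the loss?** The overall probability is P(stop at stage 1) plus, for x = 0 and 1, P(x of the first 6) × P(at least 4 − x of the second-stage patients). The plan is inconsistent on second-stage size (four more patients, but a total of 12), which is a separate matter, so both are shown. At s = 1 and s = 0.50 the result is 80.1% and 35.6% with four more patients, and 86.0% and 38.8% with six more. The loss remains either way.

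**The case against.** The strongest reply is that Section 11 already counts every grade 3-4 toxicity, so severe chills, fever, cytopenia or infection would breach the tolerability limit whatever Section 8.2 says. As a reading of 11.3.2 and 11.4.1 that is correct. It does not remove the problem: the synopsis and Section 5.1.3 set the expansion and suspension rule on DLT, nothing says which section governs, and 5.1.2 is too unclear to settle it.

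A reader might infer that severe infusion reactions and infections can never reach the DLT boundary. The documents do not support that. Item 8.2.3 restricts by organ and not by mechanism. Of the ten infusion-reaction symptoms in Section 5.5.5, breathing problems, nausea, vomiting, dizziness and headache plausibly fall in a listed class, and high blood pressure is arguable. An infection that causes grade 3 or greater toxicity in a listed organ within 30 days would count, as would a treatment-related death within the 8.2.4 window. The gap concerns events without those features.

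A reader might also infer that the gap persists whichever event name is adopted. It does not: if every section used grade 3-4 toxicity, these events would all count.

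Other safeguards are real. Grade 3-5 infusion reactions go to the safety committee, which may suspend the trial (Section 8.3, Appendix C). Sterility failure prompts clinical evaluation and FDA reporting (5.4.5, 8.5.1). Section 5.6.1 allows treatment to be discontinued for any adverse event. These are matters of judgment and do not replace the numeric rule.

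Some omissions may be deliberate, since Section 7.3 attributes lymphopenia to the leukapheresis. It also reports no attributable grade 3-4 toxicity so far, but the completed study described in Section 1.4 gave a single infusion and this trial gives three.

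**Conclusion.** The concern holds as a conflict in a decision rule. Section 8.2 covers fewer types of event than the grade 3-4 toxicity named in Sections 11.3.2 and 11.4.1, yet both carry the same limits, and two such patients among the first six are enough to separate the rules. By grade the difference runs the other way: Section 8.2 reaches grade 5, which Section 11 does not mention.

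The stated 11.4% and 76.7% are correct for the wider event only. Under the DLT rule the chance of stopping at a 40% grade 3-4 rate is lower whenever some affected patients do not meet Section 8.2. The 58.0%, 34.5% and 11.4% figures show how it depends on the share that does; they assume that share, and they assume patients are independent. It is tempting to go further and say the DLT rule would almost never stop a toxic product. That would need nearly all severe events to spare every listed organ, and the documents give no such information.

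The point should be resolved before the six-patient decision.

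**What to change.** Reconcile the synopsis and Sections 5.1.2, 5.1.3, 8.2, 8.3, 11.3.2 and 11.4.1 so that one defined event drives both the enrollment boundary and the tolerability verdict. Within that:

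- Use one term for infusion reactions in 8.2.1 and 8.3, or state how the two terms relate.
- If DLT is the chosen event, have Section 8.2 state whether grade 3 or greater counts for each class raised in 5.4.5, 5.5.5 and 7.3: infusion reaction, constitutional, hematologic, metabolic, musculoskeletal and product-related infection. If grade 3-4 toxicity is chosen, state how grade 5 is handled. Both choices rest with the investigators and safety committee.
- Clarify the grade threshold in 5.1.2.
- State the operating characteristics in Section 11 for the chosen event.

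The cost is wording, since adverse events are already recorded and graded under Section 8.1. The trade-off is that a wider event stops an acceptable product more often. If the grade 3-4 rate is 10% and half of affected patients meet Section 8.2 (an assumption), the DLT rule stops at stage 1 with probability 1 − 0.95^6 − 6(0.05)(0.95^5) = 1 − 0.7351 − 0.2321 = 3.3%, against 11.4% for the wider event. Section 11.4.1 already states 11.4% as the early-stopping probability at that rate.

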5.0 Treatment Plan

5.1 Dosing

- 5.1.1 Leukapheresis to collect PBMC for infusion will be performed the day prior to infusion. Patients will be administered three infusions of APN401 at 50×10^6 cells/kg IV, separated by 4 weeks (reference Appendix I). Leukapheresis and administration of APN401 can be delayed up to 3 weeks at the physician's discretion. Subsequent treatment must occur 28 days after prior treatment.
- 5.1.2 Six patients will be treated initially. Should >1/6 subjects experience greater than grade 3 or 4 toxicity, further enrollment of study subjects and further administration of the study agent will stop pending assessment of the risk.
- 5.1.3 If DLT is observed in $\leq 1/6$, than an additional four patients (a total of 12) will be enrolled to allow evaluation of laboratory correlates. Enrollment will be suspended if >1/6 or >3/12 patients manifest DLT

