5.7 Duration of follow-up

All patients, including those who discontinue protocol therapy early, will be followed for response until progression or one year from registration, whichever occurs first. Patients will then be followed for survival for five years from the date of registration. All patients must also be followed through completion of all protocol therapy.

Safety and Immunologic Activity of Multiple Infusions of APN401
Wake Forest Baptist Comprehensive Cancer Center
CCWFU 03716

6.0

Study Calendar

Baseline evaluations, including imaging, are to be conducted within 4 weeks prior to initiation of treatment (Day 0). In the event that the patient's condition is deteriorating, laboratory evaluations should be repeated within 48 hours prior to initiation of the next cycle of therapy.

		Treatment Phase							Follow-Up Phase		Early Termination
	Pre-Study ^J	Day 0 Week 1	Day 1 Week 1	Day 15 Week 3 (± 1 day)	Day 28 Week 5 (± 3 days)	Day 29 ^N Week 5	Day 56 Week 9 (± 3 days)	Day 57 ^N Week 9	Day 71 Week 10 (± 3 days)	Week 18 and every 8 weeks (± 1 week) ^L	Off Study Visit/Early Termination Visit ^{L,M}
Leukapheresis ^A		X			X		X				
APN401 ^B			X			X		X			
Informed consent	X										
Demographics	X										
Medical history	X										
Concurrent meds		X			X		X		X	X ^O	X
Vital signs ^C	X	X	X	X	X	X	X	X	X	X	X
Physical exam ^Q	X	X		X	X		X		X	X	X
Performance status	X	X		X	X		X		X	X	X
CBC w/diff ^D	X	X		X	X		X		X	X	X
Chemistries ^E	X	X		X	X		X		X	X	X
PT, PTT	X										
HIV, HBV, HCV	X										
βhCG ^F	X										
Adverse events		X	X	X	X	X	X	X			X
Imaging ^G	X								X ^L	X ^K	X ^L
Tumor marker ^H	X								X	X	X
Immune response ^I		X		X	X		X			X	X

A. PBMC will be harvested from the peripheral blood by a standard 1.5 to 2.0 blood volume mononuclear cell leukapheresis.

B. APN401 is infused 50 x10⁵/kg IV over 30 minutes

C. Vitals signs should include blood pressure, heart rate, temperature, and respiratory rate. At the administration visits, vital signs should also be performed before infusion and 30 and 60 minutes after the end of the infusion.

D. Hemoglobin, hematocrit, white blood cell count, and platelets. The CBC differential includes enumeration of neutrophils, lymphocytes, eosinophils, monocytes, basophils and any abnormal blood cells.

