M. Off study/early termination assessments are only indicated for patients who do not complete all study visits (until week 58) /Follow-Up phase. These assessments should occur no more than 4 weeks after the discontinuation of study treatment. If the subject had not undergone imaging within the past 6 weeks re-imaging is indicated. If a patient discontinues treatment for any reason other than progression, imaging will be done every 12 weeks until progression.

N. Must occur the day following leukapheresis day.

O. Following the week 18 visit only documentation of anti-cancer treatment.

P. Adverse events will be recorded on an ongoing basis and up to 2 months following the administration of the test drug.

Q. Physical Exam may be completed +/- 2 days of visit.

Safety and Immunologic Activity of Multiple Infusions of APN401
Wake Forest Baptist Comprehensive Cancer Center
WFBCCC 03716

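### The 30-day organ-toxicity DLT window in 8.2.3 can leave uncounted days between infusions (3 under the calendar windows, 18 if a 3-week delay lengthens the interval to 49 days)

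*Combined protocol and SAP*

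**What the plan says.** Section 8.2 defines DLT by four criteria with different time limits.

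- 8.2.1: "CTCAE grades 3-5 allergic reactions related to study cell infusion". No time limit.
- 8.2.2: "CTCAE grades 3 and greater autoimmune reactions other than that vitiligo". No time limit.
- 8.2.3: organ toxicity of grade 3 or higher, neither pre-existing nor caused by the malignancy, and "occurring within 30 days of study product infusion". The text does not say whether this means each infusion, the first or the last.
- 8.2.4: treatment-related death, with an 8-week limit.

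Section 5.1.1 plans three infusions 4 weeks apart, then says: "Leukapheresis and administration of APN401 can be delayed up to 3 weeks at the physician's discretion". The next sentence reads: "Subsequent treatment must occur 28 days after prior treatment". The protocol does not explain how the two fit together.

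The Study Calendar (section 6.0) gives the Day 28 and Day 56 leukapheresis visits a window of ±3 days. Its footnote N says of the Day 29 and Day 57 infusions: "Must occur the day following leukapheresis day".

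The stopping rules use two different event definitions. The synopsis and 5.1.3 count DLTs: at most 1 of 6 allows expansion, and more than 1 of 6 suspends enrolment. Sections 5.1.2, 11.3.2 and 11.4.1 refer instead to grade 3 or 4 toxicity, with no time window. Section 8.1 has adverse events recorded throughout and for up to 2 months after the study product.

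**The concern.** A 30-day window fits a 28-day cycle: each window runs past the next infusion, so the treatment period is fully covered. It stops fitting once an interval exceeds 31 days, and the protocol appears to allow that in two ways. A patient could then be on protocol therapy, awaiting the next infusion, and have a grade 3 organ toxicity that does not meet the DLT definition.

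The first decision turns on one event versus two in six patients, so the classification of a single event can settle it. Nothing in the protocol suggests that a pause in counting between infusions is intended. Treatment-related death is counted for 8 weeks and adverse events are recorded for 2 months.

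**Working it through.** **Convention.** The infusion day is day 0 and days 0 to 30 are inside the window. For an interval of L days to the next infusion, the uncounted whole days are days 31 to L − 1, so their number is max(0, L − 31).

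**Inputs.** Window 30 days (8.2.3). Planned spacing 28 days and permitted delay 21 days (5.1.1). Leukapheresis on Days 28 and 56, ±3 days, with infusion the next day (section 6.0). Nominal infusions on calendar Days 1, 29 and 57.

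**Planned schedule.** 29 − 1 = 28 and 57 − 29 = 28, which reproduces the 4-week spacing. max(0, 28 − 31) = 0, so there is no gap.

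**Calendar windows alone.**
- Infusions 1 and 2: the latest infusion 2 is Day 28 + 3 + 1 = 32. L = 32 − 1 = 31, uncounted 0.
- Infusions 2 and 3: the earliest infusion 2 is Day 28 − 3 + 1 = 26, and the latest infusion 3 is Day 56 + 3 + 1 = 60. L = 60 − 26 = 34, uncounted 34 − 31 = 3 (days 31 to 33).

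**Delay under 5.1.1, if it lengthens the interval.**

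| Delay | Interval L | Uncounted days |
|---|---|---|
| none | 28 | 0 |
| 1 week | 35 | 4 (31–34) |
| 2 weeks | 42 | 11 (31–41) |
| 3 weeks | 28 + 21 = 49 | 18 (31–48) |

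If the 28-day sentence in 5.1.1 binds every interval exactly, the gap is zero. In that case the delay permission has no effect on infusions 2 and 3, and the calendar's ±3 days contradict the text.

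**Which infusion starts the clock.** Per infusion is the reading kindest to the plan. If only the first infusion counted, then on the nominal schedule infusion 3 falls 56 days after infusion 1, and follow-up to 30 days beyond it ends at day 86. Days 31 to 86 would be uncounted, which is 56 days.

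**What the other criteria cover in the gap.** The 8-week limit for treatment-related death is 56 days, longer than the 49-day interval, so no day is uncovered. Allergic and autoimmune events have no limit. The remainder is organ toxicity, mainly grade 3 or 4, that is neither allergic nor autoimmune, plus deaths not judged treatment-related.

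**Consequence for the rules.** Suppose that among the first six patients one has a DLT inside the window, and another has a non-autoimmune grade 3 hepatic event on day 40 of a 49-day interval. The DLT count is 1 of 6, and 5.1.3 allows expansion. The grade 3–4 count is 2 of 6, above the limit of 1 in section 11. The same data give opposite answers.

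**The case against.** The case against has four parts.

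1. *The 49-day interval is one reading of 5.1.1.* The sentence after the delay permission fixes treatment at 28 days after the prior treatment. This stands: the 18-day figure is conditional. The 3-day figure does not need the delay clause, but it too falls away if 28 days is exact.

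2. *Most of what matters is covered elsewhere in 8.2.* This largely stands. Autoimmune toxicity, a natural late concern for an agent that silences a negative immune regulator, counts at any time. A reader might infer that any grade 3 to 5 organ toxicity in the gap is ignored; 8.2.1, 8.2.2 and 8.2.4 show otherwise.

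3. *The event is still recorded, and still counts under 5.1.2 and section 11.* This also stands, although 5.1.2 is loosely worded on the grade. It turns the problem from a missed event into two rules that can disagree. It does not remove it.

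4. *No loss of stopping probability can be shown.* A reader might infer that the 76.7% chance of stopping at stage 1 under a 40% toxicity rate must fall when days go uncounted. The documents do not support that. The 76.7% belongs to the section 11 rule, which has no window. Even if it is carried over to DLTs, the direction depends on an assumption. Take one constant daily hazard giving 40% over the undelayed 28 + 28 + 30 = 86 days. A patient with two maximal delays is at risk for 49 + 49 + 30 = 128 days, of which 128 − 36 = 92 are counted, more than 86. The counted rate is 1 − 0.6^(92/86) = 42.1%. The chance of two or more events in six becomes 77.2%, 77.8% or 79.8% with one, two or six such patients: a slight rise.

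A reader might also suppose that delays fall in the patients most likely to have a late event. That is plausible, but the protocol does not say why delays occur or how often. A grade 3 event that prompts a delay around day 28 is already inside the window.

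**Conclusion.** The point holds in a limited form. Read per infusion, 8.2.3 covers the planned 28-day schedule completely. It leaves up to 3 uncounted days between infusions 2 and 3 under the calendar windows. It leaves 18 if a 3-week delay takes an interval to 49 days. Both figures assume that the 28-day sentence in 5.1.1 is not an exact requirement.

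The events affected are mainly grade 3 or 4 organ toxicities that are neither allergic nor autoimmune. They fall outside the DLT-worded rules and inside the grade 3–4 rules, so the stopping criteria can conflict over a single event in six patients. The documents support no estimate of how often this would happen and no claim about the design's error rates. It is worth correcting because it touches the primary safety decision and the correction costs almost nothing.

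**What to change.** In 8.2.3, replace the 30-day phrase with a continuous counting period: from the first infusion until 30 days after the patient's last infusion. This settles which infusion is meant and closes the gap under either reading of 5.1.1. If every interval is exactly 28 days, it gives the same coverage as the per-infusion reading.

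Separately, the sponsor should reconcile the delay sentence in 5.1.1 with the 28-day sentence that follows it, and both with the calendar's ±3 days. Which timing rule applies is for the sponsor to decide; the change to 8.2.3 does not depend on it.

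The cost is one phrase. No new data are needed, because section 8.1 already has adverse events recorded throughout and for up to 2 months after the study product. The downside is that a few more events may count as DLT in patients with longer intervals. The change does not by itself align the DLT rules with the grade 3–4 wording of 5.1.2 and section 11, but it removes this source of disagreement between infusions.
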